The goal of this study is to test the efficacy, safety, and feasibility of the iStride™ device to correct gait asymmetry and improve gait parameters including gait speed and balance in individuals with stroke. The study will be structured around subjects walking on the device with their gait recorded and analyzed before and after device usage. The study design is within-subjects where each individual's gait will be compared before, during, and after the treatment period. The study will be conducted on chronic stroke patients in a home-based setting. The treatment will last at least four weeks with an initial visit prior to the start of treatment and several follow-up tests targeted at one month, three months, six months and twelve months post-treatment, in order to measure retention. A subset of the home study patients may be asked to continue treatment with variations in frequency and duration. In addition, several customization factors, specifically to the wheel size, may be tested in order to determine if patients plateau at any point during their rehabilitation. This is important in order to determine the most beneficial prescription for patients while using the device. Additionally, in order to assess muscle activation and response, a subset of these subjects may be asked to visit an alternate clinic site for EMG testing pre and post-treatment.

The home-based treatment will consist of at least twelve treatment sessions performed over a minimum of four weeks with a gait evaluation pretest and initial fitting of the shoe the week before. Gait evaluations will be performed the week before the first treatment and periodically during treatment (no more than once per week). Follow-up tests will be targeted at one week, one, three, six, and twelve months after the final treatment session.

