A study physician or an advanced registered nurse practitioner (ARNP), rehabilitation clinician with knowledge, or subject's physician will perform medical screening or sufficient review of a medical record for the subjects that will participate in the proposed studies. This screen will be used to determine if the potential subjects had one or more cerebral strokes without other medical conditions (e.g., other neurological, orthopedic, etc.) that would affect or explain the subjects' walking or limb movement. Clinical assessments may consist of vision, proprioception, gait analysis and cognitive screening. The 10 Meter Walk Test, Timed Up and Go Test²⁴, Berg Balance Scale, and Functional Gait Assessment tests will be performed to assess changes in subjects' gait velocity, aerobic capacity, and risk of falls, respectively, before, during, and following treatment. Additionally, several psychosocial outcomes will be tested.

To measure gait, Veristride motion sensors will be incorporated. These sensors, along with additional sensors will be used during all treatment sessions creating a complete library of data while using the device during treatment. This data will be analyzed with existing algorithms to measure gait parameters as well as assess changes that may occur as a result of iStride™ device usage. For the subjects in this study who perform treatment with caregiver supervision, these sensors will allow us to verify that the subject completed the treatment as specified. A fit bit device may also be used in this study, in order to track compliance, record telemetry-related data, as well as provide an overall collection of steps per patient.

Our main analysis will be to compare the amount of learning (i.e. deviations from symmetry post-adaptation) to normal baseline symmetry. This will be done using a repeated measures ANOVA to compare baseline gait symmetry at the start of the experiment to post-adaptation at the end of the experiment and on the follow-up assessments. We will quantify the amount of adaptation and the change in gait asymmetry by comparing the magnitude of step length and double support differences during baseline, at the beginning of treatment, during treatment, and after treatment. During a symmetric gait, step lengths on each side are the same; during an asymmetric gait, step lengths are different. These measures are standard accepted measures for measuring gait asymmetries.

4. Sample size

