Preliminary studies with three healthy test subjects showed statistical data that indicated that the minimum number of subjects for this study is 18.⁴ We powered the t-test between pre-treatment and post-treatment data. We calculated an effect size of 0.68 for step length difference, resulting in an estimated sample size of 18 subjects. The preliminary test with healthy subjects was approved under the Einstein Healthcare Network IRB HN4365, and other preliminary tests with healthy subjects were conducted under USF IRB Pro00001858.

We have no reason to think that women and men will differ in their abilities on any of these tasks. As such, we expect to enroll approximately the same number of men and women.

5. Inclusion and exclusion criteria

We will recruit individuals with stroke for this study. If eligible and willing, individuals that participated in our previous home study may be allowed continued participation. Since the focus of this project is to ultimately use this device to help stroke survivors, we will recruit both young adults and older adults.

Inclusion criteria includes:

- 1) Age 21-80
- 2) One or more cerebral strokes, but all strokes on same side
- 3) Stroke occurred at least 6 months prior to enrollment
- 4) Gait asymmetry, but able to walk independently with or without a cane
- 5) Not currently receiving physical therapy
- 6) No evidence of severe cognitive impairment that would interfere with understanding the instructions
- 7) No evidence of one-sided neglect, affecting ambulation
- 8) At least 25 feet of walking space (does not need to be a straight line)
- 9) Weight does not exceed 275lbs

Exclusion criteria includes:

- 1) Uncontrolled seizures
- 2) Metal implants (stents, clips, pacemaker)
- 3) Pregnancy
- 4) History of a neurological disorder other than stroke (Parkinson's, MS)
- 5) Chronic Obstructive Pulmonary Disease
- 6) Uncontrolled blood pressure
- 7) Head injury in the past 90 days
- 8) Myocardial infarction within the last 180 days
- 9) Cannot rely on a rolling walker for ambulation
- 10) Severe Ataxia
- 11) Previously diagnosed vestibular ear issues

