The risks for this study are slightly higher than regular walking over ground and include the possibility of falling. The risk can be compared to walking on high-heeled shoes. To minimize this risk, subjects will be screened for appropriateness of trial participation by licensed physical therapists. For subjects who may be permitted to use this device with caregiver supervision, thorough training of all caregivers will be performed and in-person or video conferencing follow-up by the physical therapist will occur as deemed necessary by the therapist. Subjects determined unable to walk safely on the device by any clinician using the device under these conditions or any reason at any time will not be allowed to continue or start the study. As such, the combined risks associated with this study are minimal.

For this home-based study, steps are taken to ensure safety. We will use a licensed physical therapist to train all caregivers to provide the appropriate level of assistance the patient needs to safely ambulate. If the patient is not able to ambulate safely on the device with caregiver supervision or the caregiver does not demonstrate the ability to safely supervise, the subject will not be allowed participation in the study. The subject will be able to call the physical therapist to discuss their progress and/or any concerns throughout the home-based treatment, at any time. To ensure a proper safety evaluation and assessment of one's home environment, the participant and their caregiver, as well as the physical therapist, must acknowledge the following within their home: proper lighting, safe hallway entrances, and removal of throw rugs and cords. Patient and caregiver will receive fall prevention education including education on the risk of falling, certain safety issues (see above), and mobility restriction. For example, the device is not to be used on stairs. In addition to fall prevention, education will be provided on movement patterns and position changes. The safety provisions will be discussed and assessed prior to the start of treatment by a licensed physical therapist.

8. The potential benefits to subjects

There is potential for subjects to improve their gait patterns, gait speed, and balance which is our hypothesis regarding this method. It may not change their gait, so there may be no benefit to subjects.

9. Human subject considerations

a. Description of the informed consent process

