The signed paper consent forms will be kept confidential and stored in a secured location. Any soft data collected will be stored in the subject's electronic record, stored in Tresorit, a fully HIPPA compliant cloud storage system, with password protection, double encryption, and limited access to only necessary personnel who are under confidentiality agreements and understand HIPPA requirements. Telemedicine modalities that may be used (9zest) are fully HIPPA compliant. The data will be anonymized and combined with data from other experiments, so the data will not be identifiable throughout the study and in all reports generated from this data.

d. Compensation

Subjects may be paid for this study. Please refer to informed consent for more detail. They will be paid within 30 days of the end of their participation in the study.

e. Withdraw from the research study

We will discontinue testing if the subject reports or we observe signs of discomfort or fatigue that interfere with their participation in the study. In any of these circumstances, the participation will immediately stop and the subject will be compensated for his/her time. Please note that the likelihood of participants experiencing these symptoms during the experiment is not greater than in their everyday lives (e.g. during walking). Since we are performing repeated-measures statistical tests, it is essential to obtain all measures from each subject. Therefore, if a subject is unable to complete the experiment, we will remove the data from analysis. Also, if a subject requests that his/her data be withdrawn, we will delete it all electronic files from our records and destroy any paper records.

10. Data and safety monitoring plan.

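### All data from subjects who do not complete are removed, so the before-after efficacy result describes only those who tolerated the device and finished, and completion is not defined

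*Combined protocol and SAP*

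**What the plan says.** Section 9e gives the rule, "if a subject is unable to complete the experiment, we will remove the data from analysis", and its reason: because the tests are repeated-measures tests, "it is essential to obtain all measures from each subject". The same paragraph stops participation when there are "signs of discomfort or fatigue that interfere with their participation in the study". Section 7 adds a safety stop: subjects whom a clinician finds unable to walk safely on the device, or for "any reason at any time will not be allowed to continue or start the study". Neither section exempts these subjects from removal.

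Section 3 places gait evaluations in the week before the first treatment and "periodically during treatment (no more than once per week". It then states: "Follow-up tests will be targeted at one week, one, three, six, and twelve months after the final treatment session". The main analysis, also in Section 3, is a repeated measures ANOVA comparing baseline with "post-adaptation at the end of the experiment and on the follow-up assessments". Section 4 bases the sample size on a narrower comparison: "We powered the t-test between pre-treatment and post-treatment data".

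The documents give no missing-data method, no all-starter analysis set, no sensitivity analysis and no dropout allowance. Section 10 mentions analysing the whole data set for all subjects, but that sentence concerns when the analysis happens and does not cancel the removal rule.

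**The concern.** There are two separate problems.

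First, the rule makes the analysis population depend on what happens after treatment starts. A subject stopped for unsafe walking, discomfort or fatigue has a baseline gait test and may have on-treatment tests, yet contributes nothing. The stated reason does not justify this: a complete-case ANOVA needs full data, but a mixed model for repeated measures does not. The study's new question is whether the device works with caregiver supervision and only intermittent therapist follow-up, so subjects who cannot manage it are relevant to the answer. The design is within-subject and the crossover without the device is optional, so no control comparison is assured.

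Second, completing the experiment is not defined. Section 3 speaks of the end of the experiment separately from follow-up, which suggests a mild reading. Section 9e wants all measures, and the planned ANOVA runs to the twelve-month visit. On that strict reading, a subject with both a pre and a post measurement leaves the pre-post comparison because of one missed late visit. Without a definition, the reading could be chosen after the data are seen.

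**Working it through.** **Inputs from the documents.** Effect size 0.68 and 18 subjects (Section 4). Pre-post t-test (Section 4). Follow-ups at one week and at one, three, six and twelve months (Section 3).

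**Assumed, because the documents do not give them.** Two-sided 5% significance and 80% target power; 18 starters; the number stopped; the stopped subjects' change relative to completers; the rate of missed visits.

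**1. The plan's sample size.** For a paired t-test, the normal approximation is n = ((1.960 + 0.842)/0.68)² = 16.97, so 17. The exact noncentral t calculation gives 19. The stated 18 lies between them. Exact power at n = 18 is 77.6%.

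**2. Power if stopped subjects are removed.** With 17, 16 or 15 of 18 left, power is 74.9%, 72.0% or 68.8%.

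**3. Completer mean against all-starter mean.** Let k of 18 starters stop, and let their true change be a fraction f of the completers' change. The completer mean exceeds the all-starter mean by 18/(18 − k + k·f) − 1.

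| f | k = 1 | k = 2 | k = 3 |
|---|---|---|---|
| 0 (no gain) | +5.9% | +12.5% | +20.0% |
| 0.5 | +2.9% | +5.9% | +9.1% |
| 1 (equal gain) | 0% | 0% | 0% |
| 1.25 (more gain) | −1.4% | −2.7% | −4.0% |

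For example, k = 3 and f = 0 gives 18/15 − 1 = 20%. The sign depends on f, and nothing in the documents fixes f.

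**4. The strict reading.** Section 3 schedules no separate end-of-treatment test, so the one-week visit may itself be the post measurement. That leaves four later visits (one, three, six and twelve months) whose loss would remove a subject with both pre and post data. If each is missed independently with probability p, the expected number kept is 18(1 − p)⁴. Power is averaged over the binomial number kept.

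| p | (1 − p)⁴ | Mean kept of 18 | Mean power |
|---|---|---|---|
| 2% | 0.922 | 16.6 | 74% |
| 5% | 0.815 | 14.7 | 67% |
| 10% | 0.656 | 11.8 | 56% |

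**5. What a mixed model would and would not do.** A simulation of 8000 trials used 18 subjects, 3 of them stopped with true change 0, completers at 0.68, three gait tests (baseline, mid-treatment, post) and equal correlation of 0.5 to 0.85. The true all-starter mean is 15 × 0.68/18 = 0.567.

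- Complete-case estimate: 0.67 to 0.68.
- Maximum likelihood, stopped subjects with baseline only: 0.67 to 0.68.
- Maximum likelihood, stopped subjects with one on-treatment test: 0.65 to 0.66.
- Stopped subjects' change set to zero: 0.56 to 0.57.

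The last result agrees with the truth because the simulation gave stopped subjects zero change. It shows what the sensitivity analysis measures and does not show that zero is the right value.

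**The case against.** The strongest reply is that few subjects will be stopped. Section 1 reports one adverse event and no safety stop among 15 earlier users, and Section 9e asserts that discomfort or fatigue is no likelier than in daily life. At one stop in 18, the overstatement is 0% to 6% for f between 0 and 1. This limits the likely size. However, the earlier users always had a therapist present, which this study relaxes, and the statement in Section 9e is the sponsor's expectation.

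A second reply is that a mixed model does not remove tolerance-related bias. That is correct, as step 5 shows. Early stops are also plausible: 14 of the 22 hands-on interventions in the earlier study came at the first session, and gait is tested at most weekly, so a stopped subject may well have a baseline test only. The mixed model is worth adopting because it stops discarding data; the sensitivity analysis is what addresses stopping.

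A third reply concerns the power figures. Section 4 calls 18 a minimum, so more may be enrolled. Missed visits tend to cluster in the same people, which would leave more complete cases than independence implies. Both points stand, and the strict-reading figures are illustrative.

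A reader might also infer three stronger things:

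- That the rule probably favours the device. No text links tolerance to gait change.
- That the before-after gait change is the only efficacy evidence. Walking speed, mobility and balance tests are also planned and a crossover is possible, although the removal rule may reach these too.
- That safety data on stopped subjects are dropped. Section 9e ties removal to the repeated-measures tests and does not say that adverse events go unreported.

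**Conclusion.** The point holds as a defect in the analysis population. As written, the plan yields a completers-only efficacy result on a mistaken statistical ground, with completion undefined and no analysis that restores the stopped subjects.

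The direction and size of any bias are unknown. With 1 to 3 of 18 stopped (assumed), the range runs from a 20% overstatement (three stopped, no gain) through zero (equal gain) to a 4% understatement (three stopped, a quarter more gain). If stopping is unrelated to gait change, the only cost is power.

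The strict reading adds an avoidable loss: about 74%, 67% or 56% power against 78%, assuming 18 starters, four later visits missed independently by 2%, 5% or 10%, and a two-sided 5% test. The milder reading avoids this loss, but the plan does not choose between them. The change is worth making before data are analysed.

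**What to change.** 1. Delete the removal rule in Section 9e. Define the efficacy set as everyone who starts device sessions, and use all their collected gait data.
2. Replace the complete-case ANOVA with a mixed model for repeated measures. With about 18 subjects and a number of gait tests that the plan does not fix, prespecify a simple covariance (for example a random subject intercept) and small-sample degrees of freedom. Its main purpose is to stop discarding data.
3. State that a missed follow-up visit does not remove earlier data, and say which visit supplies the post measurement.
4. Add a sensitivity analysis that sets change to zero for subjects stopped with no post-baseline gait test. Report it with the number stopped and the reasons.
5. Keep deletion at a subject's own request as it stands.

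The cost is protocol wording, a change of model, one sensitivity analysis and a short account of who stopped and why. No extra subjects or visits are needed. The reported efficacy may be less favourable.

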Upon initial contact, the principal investigator will conduct a phone interview and the investigator will send the consent form to potential subjects. This will allow them an opportunity to review eligibility criteria and the consent form without feeling rushed and will give them a better opportunity to discuss study participation with a friend or family member.

The potential subject will be given ample time to consider their participation in the study and to ask any questions he or she may have. If the individual agrees to participate, they will sign all informed consent documents and be given a copy to retain.

The written consent form will contain all of the elements required by the Western Institutional Review Board (WIRB) as well as adherence to all federal requirements. The primary information

on the consent form will include, but is not limited to, name of sponsor, explicit study procedures, risks and benefits, subject rights, consent to use data, and study contact information. Each page will contain the most recent stamped WIRB approval printed on each page of the form. It will be written in language that is understandable to the subject. The original signed consent form, if done using paper, will be retained in the study subject's file in a locked filing cabinet in the office of a study staff member, and stored for a period of 5-years in accordance with WIRB policy after which time paper records will be shredded. The original signed form may also be produced using a certified electronic signature program, Hellosign, which produces legal, executed, documents. These will be retained in the subject's electronic record, stored in Tresorit, a fully HIPPA compliant cloud storage system, as well for 5-years.

b. Safeguards to protect potentially vulnerable subjects

All subjects for this study will have at least normal cognitive function as described in the inclusion requirements. Care will be taken to make sure potential subjects understand the risks and that they may not receive any benefits from this study.

c. Privacy and confidentiality

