The collected data will be coded so no personally identifying information will ever be attached to the data. The lookup table will be stored separately from the data. Only [name], [name], and [name] will have access to the data and the lookup table. No one but the PI ([name]) and study staff will have access to the data used in this study. The data will be recorded to spreadsheet and/or text files. Shortly after the experiment, the data will be analyzed for completeness and integrity. It will then be copied to a remote secure server and backed up. Once a subject's experiment has been verified, it will only be looked at as part of all experiments performed in conjunction with this set of experiments, all of which will be anonymous. The analysis of the entire data set (all subjects) will occur after each experiment.

11. Research funding information

This study will be funded by Moterum Technologies Inc., which is a company that evaluates technologies related to rehabilitation with the intention of commercializing viable technologies and bringing them to market.

Moterum Technologies Inc. has licensed two patents from USF, which have [name] and [name] listed as the inventors:

USF 13B154PR [name] filed in Feb. 2014: "SYSTEMS AND METHODS FOR DESIGNING KINETIC SHAPES". This is a provisional patent for a method to generate a spiral-shaped wheel that generates a known horizontal force or moment when a vertical force is applied on it. It can be used to specify the shape of wheels that redirect forces and can also be used to define the roll-over shape of a foot with the ground to alter the interaction and resulting gait.

USF 11B170PR filed in Feb. 2012: "GAIT ALTERING SHOE". This patent is for a shoe that generates a backward or forward motion when the user steps down on the shoe. The shoe can be used for rehabilitation of individuals with stroke, specifically for correcting their asymmetric gait, and also for healthy individuals to increase their forward progression with each step.

In addition to the patents, [name] has been asked to serve on the Advisory Board for Moterum Technologies Inc, which includes a yearly honorarium and stock options in the company. A conflict of interest management plan has been put in place and approved by USF and the WIRB.

Research References

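### Section 9e erases all of a participant's records on request, with no exemption for falls, adverse events, device exposure or disposition, so exposed people can vanish from the safety results beyond recovery

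*Combined protocol and SAP*

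**What the plan says.** Section 9e (Withdraw from the research study) contains two different rules.

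- Non-completion: "if a subject is unable to complete the experiment, we will remove the data from analysis". This governs the analysis; it does not mention destroying anything.
- A request to withdraw data: "if a subject requests that his/her data be withdrawn, we will delete it all electronic files from our records and destroy any paper records". This governs the source record. It sets no time limit, lists no exemption and does not ask for the deletion to be recorded.

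Two other sections bear on the second rule. Section 9a (informed consent process) sets a retention period for the signed consent form. The paper form is "stored for a period of 5-years in accordance with WIRB policy after which time paper records will be shredded", and the electronically signed form is kept in the subject's electronic record for the same time. Section 10 (Data and safety monitoring plan) has the coded data checked soon after the experiment, and then "It will then be copied to a remote secure server and backed up". It adds that "The lookup table will be stored separately from the data".

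Section 3 names safety among the study goals, beside efficacy and feasibility. Section 7 names falling as a risk. Section 2 says the study is to assess caregiver supervision with only intermittent physical-therapist follow-up.

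**The concern.** Data left out of an analysis can be put back in a sensitivity analysis. Data that have been destroyed cannot. If someone who has fallen asks for their data to be withdrawn, following 9e to the letter leaves no event, no exposure and no reason for leaving. The safety results would then describe a smaller group in which that event never happened, and a reader could not tell that anyone was missing, because nothing requires even a count of such requests.

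This matters more than usual here. The planned sample is 18, so a single event is a large part of the safety evidence. The main safety question, whether caregivers can supervise in place of a therapist who is always present, depends on a handful of rare events.

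**Working it through.** The point is mainly textual. The arithmetic only shows scale.

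**1. What each rule in 9e does**

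| Participant | Efficacy analysis | Source record |
|---|---|---|
| Non-completer, no request | Dropped by the non-completion rule | Survives |
| Non-completer who asks for data withdrawal | Already dropped; no further change | Destroyed |
| Completer who later asks | Lost because of the deletion rule | Destroyed |

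The deletion rule adds to the efficacy problem only in the third row. For safety it adds to the second and third rows, because in the first row any fall is still on file and can be reported.

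**2. What the five-year period covers**

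- Section 9a, paper: "The original signed consent form, if done using paper, will be retained" for five years.
- Section 9a, electronic: "The original signed form may also be produced using a certified electronic signature program", and it is also kept for five years in the subject's electronic record.
- Section 9c, collected data: "Any soft data collected will be stored in" that same electronic record. No period is given.
- Section 10: coding, checking, copying and backup of the data. No period is given.

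Taken literally, 9e's deletion of every electronic file and any paper record includes the consent form. For outcome, sensor and safety data there is no stated period for 9e to contradict.

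**3. Safety illustration**

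Inputs, from section 1: 15 users in the preceding home study and one recorded adverse event (dizziness with a controlled fall to a chair, no injury). Suppose, purely for illustration, that this user had asked for deletion. Exact (Clopper-Pearson) two-sided 95% intervals:

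- As recorded: 1/15 = 6.7% (0.2% to 31.9%).
- After deletion: 0/14 = 0%, with upper limit 1 − 0.025^(1/14) = 23.2%.

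The intervals overlap heavily. What is lost is the only event. At the planned size, one deletion is 1/18 = 5.6% of the sample.

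**4. Efficacy illustration**

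Inputs, from section 4: effect size 0.68, pre/post t-test, 18 subjects. Alpha, sidedness and power are not stated, so two-sided 0.05 and 80% are assumed.

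- Reproducing the plan's figure: the normal approximation is ((1.960 + 0.842)/0.68)² = 16.98, rounded up to 17; the noncentral t gives 19. The stated 18 lies between them. Power at 18 is 77.6%.
- Deletion unrelated to outcome: power is 74.9%, 72.0% or 68.8% after 1, 2 or 3 deletions.
- Extreme case: all 18 complete, there is no true effect, paired differences are normal, and the k poorest responders ask for deletion. The one-sample t statistic is computed on the remaining 18 − k values and compared with the 97.5% point on 17 − k degrees of freedom (200,000 simulated trials).

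| Deleted (k) | Shift in mean (SD) | Chance of a false significant benefit |
|---|---|---|
| 0 | 0 | 2.5% |
| 1 | +0.11 | 7.9% |
| 2 | +0.20 | 16.3% |
| 3 | +0.28 | 27.0% |

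These show how strongly so small a sample responds to selective deletion. They are not forecasts, because the plan gives no deletion rate and no reason to expect the poorest responders to be the ones who ask.

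**The case against.** Several objections are sound and limit the point.

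- **Retention.** A reader might infer that 9e conflicts with a five-year retention of all study records. The documents do not support that: the period in 9a is written for the signed consent form only. Nor is it certain that a site cannot obey both sections. Section 9c treats consent forms and collected data separately, so 9e can be read in context as covering only the data. The literal wording still reaches the consent form, and a short clarification would settle it.
- **Timing and direction.** A reader might infer that the rule favours the device by removing bad outcomes once they are known. Section 9e is silent on timing, so late requests are allowed, but so are early ones. The participant makes the request, not the study team. That people who fall or see no benefit would ask more often is plausible but undocumented. The funder has a commercial interest, but section 11 also reports an approved conflict-of-interest management plan.
- **Completed analyses.** Section 10 has the full data set analysed after each experiment, so results may exist before a request. The plan does not say that finished analyses would be rerun.
- **Overlap.** Much of the efficacy bias from people who leave comes from the non-completion rule. That is right, and the efficacy claim here is confined to completers.
- **Participant choice.** Erasure on request protects participants, and ending it for all coded data would be an ethics decision as much as a statistical one. For that reason the fix below is narrow.
- **Unseen consent form.** Limits on data withdrawal may be set out in the consent form, which was not available for this review. If so, 9e should match it.

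None of this supplies the missing exemption for safety, exposure and disposition.

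**Conclusion.** The point holds in a limited form. As written, 9e lets a recorded fall or adverse event, together with that person's exposure and disposition, be removed beyond recovery in a study of about 18 people that has safety as a goal. It is a stated rule with a poor consequence, not merely a missing detail. The efficacy effect is restricted to completers who later ask, and the retention conflict is restricted to the signed consent form.

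The size is unknown. One event in 15 becoming none in 14, and the simulated error rates, rest on assumed requests; the simulation further assumes that the poorest responders are the ones who ask. The conclusion depends on neither. It needs only that 9e be followed as worded and that at least one person with a relevant safety record makes a request. Label: cheap improvement.

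**What to change.** Amend the data-withdrawal sentence in 9e so that, on such a request:

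1. no further data are collected;
2. a coded record is kept and reported of safety events, device exposure, the date of leaving and, if given, the reason, up to that date;
3. the number of data withdrawals is reported with the results;
4. the signed consent form is kept for five years, as in section 9a;
5. identifiers and the lookup-table entry are handled as WIRB requires.

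Explain this in the consent form. Efficacy data can still be erased on request under this wording; the count in item 3 then tells readers how many people are missing. Because the lookup table is already held apart from the coded data, the retained record need not carry direct identifiers.

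The cost is a wording change to the protocol and consent form, with WIRB approval. The downside is that participants lose the option of erasing this limited coded record, which must be made clear before they sign.
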